(1.51) calculated based on the results of a previous study ⁽²⁵⁾. the predicted sample size (n) was a total of (24) cases (i.e. 12 cases per group). Sample size was increased by 20% to compensate for possible dropouts during follow-up intervals to be (30) cases (i.e. 10 cases per group). Sample size calculation was performed using G*Power version 3.1.9.7⁽²⁸⁾

iii. Assignment of intervention:

a. Randomization and Allocation concealment.

1- Type: block Randomization, with blocks numbers of 10 and 1:1:1 allocation ratio in to 3 groups

Group I: DDM (study)

Group II: (control) blood clot

Group III: (+ control) blood clot with collagen

2- Sequence generation: the most senior supervisor will generate the sequence of random numbers using online randomization (www.random.org).

Allocation concealment and implementation:

Allocation concealment will be ensured by preparing opaque envelopes containing one number from the generated random sequence for assigned group. The most senior supervisor will select an envelope and reveal the treatment group at the final regeneration visit.

b. Blinding:

double blind study, participants, outcome assessors, statistician will be blinded.

iv. Study setting

This study will be conducted at the Outpatients Clinic at the Department of Pediatric Dentistry and Dental Public Health, Faculty of Dentistry, Ain Shams University.

ii. Study methodology

ethical regulation:

The study protocol will be submitted to the Research ethics committee, Faculty of Dentistry, Ain Shams University for approval.

V. Population

All parent or legal guardian fulfill the eligible criteria will be signed an informed consent before beginning any procedure, explaining detailed treatment procedures, the possible outcomes, comprehensive discussions of the risks, complications, alternative treatment options, follow-up period needed, and sequel of no treatment⁽⁸⁻¹⁴⁾.

Inclusion criteria:

- (1) Age 7–13 years at the time of enrolment.
- (2) Provision of informed consent by one parent or legal guardian.
- (3) At least one immature permanent anterior tooth diagnosed with irreversible pulpitis or pulp necrosis with or without periapical lesions.
- (4) Restorable teeth.
- (5) Compliant patient/parent.
- (6) Patients not allergic to medicaments and antibiotics necessary to complete procedure (ASA 1 or 2).
- (7) Radiologic evidence of open apices (Teeth are considered immature when a minimum of 1 mm apical foramen width is evident)

Exclusion criteria

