- (1) Teeth with root fractures or split roots.
- (2) Presence of root resorptions.
- (3) Presence of periodontal pockets.
- (4) Developmental anomalies
- (5) Presence of periapical radiolucency more than 10 mm
- (6) Tooth with class III mobility.

vi. Clinical Procedures

a. Screening Recruitment

Patients attending the outpatient's clinic of the Pediatric Dentistry and Dental Public Health Department, Ain Shams University will be screened for eligibility. Only patients who met the inclusion criteria and sign the informed consent will be conveniently enrolled in the study until

the predetermined sample size is reached. All examination procedures will be done by the same operator to ensure standardization.

b. Informed Consent

A signed informed consent from parent or legal guardian, and an oral assent to the child, as outlined by the Research Ethics Committee, Faculty of Dentistry, Ain Shams University will be obtained before the conduction of the study.

Grouping:

Eligible immature anterior teeth will be randomly allocated in two groups:

Group I: 10 teeth will be treated with demineralized dentin matrix as scaffold in regenerative endodontic procedure.

Group II: 10 teeth will be treated with conventional regenerative endodontic procedure (blood clot scaffold).

Group III: 10 teeth will be treated with regenerative endodontic procedure (bloodclot and collagen scaffold).

Clinical procedures:

Pre-operative periapical radiograph and cone beam computed tomography CBCT will be taken on the selected non-vital tooth in each child before the beginning of the regenerative endodontic treatment procedure (29, 30).

RET will be carried out according to ASE⁽⁸⁾

First Appointment

- Local analgesia will be delivered (2% lidocaine with 1:100,000 adrenaline).
- Following rubber dam isolation and access cavity preparation, pulp tissue extirpation/debridement
- The root canal system will be minimally instrumented.
- Copious irrigation will be performed, gently with 20ml NaOCl (1.5% NaOCl (20mL/canal, 5 min) using 0.3mm gauge single side vented needles, adjusted 3 mm short of the apex.
- then canal will be irrigated with EDTA (20 mL/canal, 5 min), with irrigating needle that will be positioned about 1 mm shorter than the root end, to minimize cytotoxicity to stem cells in the apical tissues, followed by a final rinse 20 mL sterile saline .

- Canals will be dried with paper points.

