double antibiotic paste, ciprofloxacin (Ciprocin 250mg tablets) and Metronidazole (Flagyl 500mg tablets) in a 1:1 ratio will be mixed with sterile distilled water in a 3:1 ratio, then will be introduced into the root canal systems using 18 G hypodermic needle and will be packed gently down the root canal using a hand plunger, ensuring that there will be no remains coronal to CEJ

- A sterile dry cotton pellet will be placed over the paste after which the tooth will be sealed with 3-4mm of a temporary restorative material.
- Patient will be dismissed for 2 week

Second Appointment (two week after 1st visit)

- Response to initial treatment will be assessed. If there are signs/symptoms of persistent infection, additional treatment time with antimicrobial.
- Local Anesthesia without vasoconstrictor will be administered; dental dam isolation will be achieved.
- Copious gentle irrigation will be performed with 20ml of 17% EDTA, followed by a final rinse 20 mL sterile saline.
- Canals will be dried with paper points.

In group I: teeth will be treated with demineralized dentin matrix as scaffold in regenerative endodontic procedure

Teeth, in this group, will be anaesthetised using a local anaesthetic without vasoconstrictor. Demineralized dentin matrix will be introduced inside the root canal and bleeding will be created into root canal by over-instrumentation by rotating K-file at 2 mm past the apical foramen with the goal of having the entire canal filled with blood to the level of the cemento-enamel junction.

A lightly moistened sterile cotton pellet will be placed into the canal, 3-4 mm apical to the CEJ, for 7-10 minutes to allow blood clot formation.

Placement of the bioactive and restorative materials: A bioactive material such as tricalcium silicate will be placed over the blood clot as a capping material. A 3-4 mm layer of glass ionomer will be gently placed over the capping material.

Followed by resin composite restoration ⁽¹⁶⁾.

In group II: teeth will be treated with conventional regenerative endodontic procedure (blood clot scaffold).

Teeth, in this group, will be anaesthetised using a local anaesthetic without vasoconstrictor. Bleeding will be created into root canal by over-instrumentation

A lightly moistened sterile cotton pellet will be placed into the canal, 3-4 mm apical to the CEJ, for 7-10 minutes to allow blood clot formation.

Placement of the bioactive and restorative materials as mentioned above.

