In group III: teeth will be treated with conventional regenerative endodontic procedure (blood clot and collagen scaffold).

Teeth, in this group, will be anaesthetised using a local anaesthetic without vasoconstrictor. Bleeding will be created into root canal by over-instrumentation

A collagen will be placed into the canal, apical to the CEJ.

Placement of the bioactive and restorative materials as mentioned above

e. Follow up

Clinical and Radiographic examination will be carried out during follow up period^(15, 16).

1- Clinical evaluation: Treatment success will be assessed using following criteria of success.

Criteria of success: Absence of

- Pain
- Soft tissue swelling
- Soft tissue inflammation
- Sinus tract
- tenderness to percussion
- tooth mobility

2- Radiographic evaluation:

A-Conventional radiographic evaluation:

Criteria of success:

- Apical foramen width reduction
- Increased dentinal wall thickness
- Increased root length
- Conventional radiograph showing progress bone healing and presence of a normal periodontal ligament space.
- Reduction in size of the lesion.

B- CBCT evaluation:

- CBC with limited field of view will be carried out at 12 month to asses dentin width and length^(23, 28)

f. Outcome measurement

Outcome	assessment	Assessment method
Primary outcome	1- pain 2-pain percussion 3-pathological mobility 4- gingival becket	1-visual assessment 2-percussion test 3-blunt ends of two examination mirrors 4-graduated metal periodontal probe
Secondary out com	1-Root length 2-Root dentinal thickness 3- Apical foramen width 4- Total radiographic root area (absence of internal and external root resorption, widening of periodontal ligament space, new preabical radiolucencies or enlargement of pre-existing lesion, pulp canal calcification)	Digital periapical radiograph examination with using paralleling device
Secondary outcome	Increased root wall thickness and increased root length.	CBCT with limited field of view

VII. Statistical analysis

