Categorical data will be represented as frequency (n) and percentage (%) and will be analyzed using chi square test. Numerical data will be explored for normality by checking the data distribution, calculating the mean and median values and using Kolmogorov-Smirnov and Shapiro-Wilk tests. If the data was found to be normally distributed, it will be presented as mean and standard deviation values and paired t-test will be used for the analysis. If the assumption of normality was found to be violated; the data will be presented as median and range values and will be analyzed using Signed rank test. The significance level will be set at $p \leq 0.05$ for all tests. Statistical analysis will be performed with IBM SPSS Statistics Version 26 for Windows.

VIII. Study timeline

This study will be conducted from October 2023 to October 2024.

X. Patient withdrawal

- Patients who aren't willing to continue in the study will have the right to quit at any time without loss of any benefits.
- Patients who don't comply with the oral hygiene measures given will be excluded from the study and will be offered to continue dental treatment at the departments' outpatient clinic.
- Any adverse event will be recorded and managed promptly. In addition, in failure occurs, the use of the experimental material will be stopped and patients will be treated with another modality.

[figure not shown]
xi. Data management

Patient information will be guarded as confidential information that should never be revealed at all times.

All information will be kept as a hard and soft copy.

xii. Adverse event reporting

Regenerative treatment is not expected to have any adverse side effects on health but if failure occurs in the regenerative treatment, conventional regenerative endodontic treatment will be fabricated.

xiii. Ethics and dissemination

a. Research ethics approval:

This protocol and the template informed consent form contained in Appendix are written following the guidelines outlined by the Research Ethics Committee and Institutional Review Board, Faculty of Dentistry, Ain Shams University.

b. Protocol amendments:

In case of protocol modifications, the Research Ethics Committee and Institutional Review Board, Faculty of Dentistry, Ain Shams University will review and approve the changes of protocol before proceeding and implementation of changes.

c. Informed consent:

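### Section X removes children for oral-hygiene non-compliance without limiting this to the time before the group is revealed, so the comparison may no longer be as randomised

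*Protocol*

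**What the plan says.** Section X (Patient withdrawal) deals with voluntary withdrawal first: families "will have the right to quit at any time without loss of any benefits". A separate bullet then says that patients who do not "comply with the oral hygiene measures given will be excluded from the study and will be offered to continue dental treatment". The care offered is in the department's own outpatient clinic. That bullet has no time limit. The readable text does not provide for any study assessment after such an exclusion.

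Four other places bear on it:

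- **Inclusion criteria.** Compliance of patient and parent is already an entry requirement.
- **Allocation concealment and implementation.** The senior supervisor "will select an envelope and reveal the treatment group at the final regeneration visit". Under Clinical procedures, the second appointment follows the first by two weeks, or by more if antimicrobial treatment is extended.
- **Follow up.** "Clinical and Radiographic examination will be carried out during follow up period", and CBCT "with limited field of view will be carried out at 12 month". The aim of the study sets one year as the period of comparison.
- **Blinding.** The text reads "double blind study, participants, outcome assessors, statistician will be blinded". The operator is not in that list.

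**The concern.** Because compliance is already screened at entry, the bullet in section X acts on children who have been enrolled. With no time limit, it covers children whose group has been revealed and whose tooth has been treated. For them, leaving the trial depends on behaviour after randomisation.

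That behaviour may be related to the outcomes. Absence of soft-tissue inflammation is one of the clinical success criteria, and one primary item is measured with a periodontal probe.

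At stake is the main benefit of randomisation: that the groups compared at one year are the groups that were formed by chance. An analysis plan can define analysis sets and handle missing outcomes, but it cannot recover examinations that were never made. With 10 teeth per arm (Grouping), each exclusion removes a tenth of an arm.

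**Working it through.** **1. The plan's own numbers.** The sample size section gives d = 1.51, two-sided alpha 0.05, 80% power, a total of 24, and a 20% increase to 30 (10 per arm). A two-sample t-test needs 8 per arm (power 0.802). Then 3 × 8 = 24 and 24 / (1 − 0.2) = 30, so both totals reproduce. Pairwise power is 0.891 with 10 per arm, 0.852 with 9, 0.802 with 8 and 0.737 with 7. Exclusions for hygiene use up the same allowance of two per arm as ordinary dropout.

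**2. When exclusion distorts the comparison.** Let p be the true success proportion in an arm, and let qS and qF be the chances that a success and a failure are excluded. Then

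observed odds of success = [p / (1 − p)] × [(1 − qS) / (1 − qF)].

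The odds ratio between arms is distorted only if the second factor differs between them. The protocol gives no value for p, qS or qF, so **every rate below is an assumption**.

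- *Exclusion unrelated to outcome (qS = qF), true 70% in both arms.* Expected 70% v 70%, no gap.
- *Equal outcome-related exclusion, true 70% in both arms.* With 20% excluded and failures twice as likely to go, qS = 0.2 / (0.7 + 0.3 × 2) = 0.154 and qF = 0.308. Observed success = 0.7 × (1 − 0.154) / 0.8 = 74.0% in both arms, no gap.
- *The same qS and qF in both arms, true 90% v 70%.* Observed 91.7% v 74.0%. The difference shrinks from 20 to 17.6 points. The odds ratio is (0.9/0.1) / (0.7/0.3) = 3.86 before and after.
- *Outcome-related exclusion in one arm only, true 70% in both.* Observed 74.0% v 70%, a false gap of 4.0 points.
- *Failures excluded in one arm only, no successes excluded.* Observed success = p / [p + (1 − p)(1 − qF)]. For p from 70% to 90% and qF from 25% to 50%, the false gap runs from 2.3 to 12.4 points.

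**3. Whole teeth, assuming 7/10 successes in both arms and exclusions in one arm only.**

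| Excluded | Observed | Gap (points) | Uncorrected chi-square p |
|---|---|---|---|
| One failure | 7/9 v 7/10 | +7.8 | not computed |
| Two failures | 7/8 v 7/10 | +17.5 | 0.375 |
| Two successes | 5/8 v 7/10 | −7.5 | 0.737 |

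For the two-failure row, chi-square = 18 × (7 × 3 − 1 × 7)² / (8 × 10 × 14 × 4) = 0.79; Fisher's exact test gives p = 0.59. That row is an extreme case. If two of ten teeth with three failures were excluded at random, the chance that both are failures is C(3,2) / C(10,2) = 3/45 = 6.7%.

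**The case against.** The strongest reply is that the harmful mechanism is not in the text. Participants are said to be blinded, so knowing the arm should not change a child's brushing. If a sore tooth leads to poor hygiene in the same way in every arm, step 2 shows no false gap under equal true rates and an unchanged odds ratio otherwise. Screening for compliance should keep exclusions few, and the 20% allowance covers two losses per arm. Much of this stands. It limits the probability of harm and answers the loss of numbers, but an allowance for numbers does not correct selection.

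Several stronger readings are tempting and are not supported:

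- *An unblinded operator decides who is excluded.* The operator is not listed as blinded, but no one is named as judge of compliance. The sentence "All examination procedures will be done by the same operator to ensure standardization" stands under Screening Recruitment and may cover screening only.
- *Nearly all exclusions would fall after allocation.* About 96% of the calendar period does (50/52 or 52/54 weeks, slightly less if the second visit is delayed). That is a share of time, not of exclusions. Nothing says when hygiene is checked, and non-compliance could show early.
- *The hygiene measures are undefined.* The readable text gives no content or threshold, but a figure after section X is not shown and the consent pages were removed. The silence carries little weight.
- *The rule should be struck out altogether.* Before the envelope is opened there is no assigned arm, and exclusion then does not cause this bias.

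An analysis plan that is not shown may define the analysis sets. It still could not supply visits that the protocol has ended.

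**Conclusion.** The point holds in a limited form. As written, section X permits randomised teeth to be removed for behaviour after allocation that may be related to the gingival and soft-tissue outcomes. It makes no provision for assessing them afterwards. The comparison may therefore cease to be as randomised.

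Neither the size nor the direction can be derived from the protocol. Under the assumed rates, the result ranges from no false gap, through a few points, to 17.5 points in a deliberately extreme case, and it can go either way. A reader might infer that the rule favours the demineralized dentin matrix arm or would produce a false significant result. The calculations show neither: the extreme case gives p = 0.375. They treat success as binary, and no link between hygiene and root length, dentinal thickness or apical width is claimed.

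The change should be made because it removes an avoidable risk at little cost, not because a bias has been demonstrated.

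**What to change.** Limit the exclusion in section X to the time before the group is revealed. Suggested wording: *Before the treatment group is revealed, a child who does not follow the oral-hygiene instructions may be excluded. Once the group has been revealed, such non-compliance is recorded as a protocol deviation. The child remains in the scheduled outcome assessments, and the tooth is analysed in its assigned arm, unless consent is withdrawn.*

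An analysis restricted to compliers should appear at most as a sensitivity analysis. The offer of dental care is unchanged, and so is every sample-size figure.

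The cost is a short edit to section X and follow-up of a few less cooperative children at visits already planned for all participants. The outpatient clinic where their care would continue is also the study setting, so continued assessment is practicable.
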